## 8.2 SAFETY AND OTHER ASSESSMENTS

Patients presenting to MUHC emergency department for cold and flu-like symptoms during the study period will be assessed for eligibility by the admitting physician based on protocol inclusion and exclusion criteria as previously detailed. Standard evaluation and collection of patient overall health status including past medical history, vital signs, physical exam, necessary imaging, and laboratory assessment will be completed as part of routine care associated with the emergency department visit. Patients enrolled into the study will be randomized and provided study drug the same day of their emergency department visit such that patients will not discharge from the emergency department until they have received their study drug and corresponding instructions for study participation. Testing results including COVID-19 status or positive influenza will be communicated via telephone contact to study patients as part of routine care follow-up and in accordance with MUHC emergency department

procedures. Patients meeting exclusion criteria following results of study related testing information will be instructed to discontinue study intervention and follow-up with their primary care provider or other non-study related healthcare provider for appropriate management.

Upon receiving study drug and following discharge from the emergency department study subjects will begin self-administering study product as outlined in section 6.1.2 of this protocol the evening of the day of enrollment. Research staff from the MUHC emergency department will begin contacting patients the following day and daily thereafter for a total of seven consecutive days as described in section 1.3 of this protocol. The following data elements are to be collected each day via telephone visits for the safety endpoints:

Safety endpoints:

Adverse Effect	Yes or No
nausea	
vomiting	
indigestion	
worsening of shortness of breath or difficulty breathing	
allergic reaction skin rash hives swelling of lips or tongue	
hospitalized or physician visit for study drug related adverse effect	

Additional data elements to be collected with each daily telephone visit that do not pertain to the primary and secondary endpoints, but remain clinically relevant include patient reported use of any OTC cough and cold medicine(s) for which MUHC emergency department research staff will record the number of the different products used, each product(s) name, and the number of doses of each product taken by the patient. Patients will be encouraged to record their OTC medication use using a 'sick' diary, but this will not be a formal requirement of the protocol. Study subjects will also be asked about how many doses were missed in the preceding 24 hours during the daily telephone visits conducted MUHC emergency department research staff. For patients that withdraw early from the study the following information will be collected at their last visit if possible:

- Date of study discontinuation
- Reason for discontinuation
- Number of study days completed prior to discontinuation of treatment/study withdrawal
- Total number of patient-reported doses taken of study drug prior to discontinuation of treatment/study withdrawal

Relevant patient demographic information including: age, sex, ethnicity, history of asthma, COPD, diabetes, COVID-19 status, hospitalization for respiratory condition within the past year will be obtained using existing health record data.

Study subjects participating in blood sampling procedures will not be contacted daily for collection of pre-defined safety assessments.

## 8.3 ADVERSE EVENTS AND SERIOUS ADVERSE EVENTS

### 8.3.1 DEFINITION OF ADVERSE EVENTS (AE)

Adverse event means any untoward medical occurrence associated with the use of an intervention in humans, whether or not considered intervention-related (21 CFR 312.32 (a)).

### 8.3.2 DEFINITION OF SERIOUS ADVERSE EVENTS (SAE)

An adverse event or suspected adverse reaction is considered "serious" if, in the view of either the investigator or Independent Safety Monitor, it results in any of the following outcomes: Death, a life-threatening adverse event, inpatient hospitalization or prolongation of existing hospitalization, a persistent or significant incapacity or substantial disruption of the ability to conduct normal life functions, or a congenital anomaly/birth defect. Important medical events that may not result in death, be life-threatening, or require hospitalization may be considered serious when, based upon appropriate medical judgment, they may jeopardize the patient or subject and may require medical or surgical intervention to prevent one of the outcomes listed in this definition. Examples of such medical events include allergic bronchospasm requiring intensive treatment in an emergency room or at home, blood dyscrasias or convulsions that do not result in inpatient hospitalization, or the development of drug dependency or drug abuse (21CFR312.32).

#### 8.3.2.1 EXPECTEDNESS

The principle investigator along with co-investigators will be responsible for determining whether an adverse event (AE) is expected or unexpected. An AE will be considered unexpected if the nature, severity, or frequency of the event is not consistent with the risk information previously described for the study intervention.

## 8.3.3 CLASSIFICATION OF AN ADVERSE EVENT

### 8.3.3.1 SEVERITY OF EVENT

For adverse events (AEs) not included in the protocol defined grading system, the following guidelines will be used to describe severity.

- **MILD:** Awareness of signs or symptoms, but easily tolerated and are of minor irritant type causing no loss of time from normal activities. Symptoms do not require therapy or a medical evaluation; signs and symptoms are transient.

- MODERATE: Events introduce a low level of inconvenience or concern to the participant and may interfere with daily activities, but are usually improved by simple therapeutic measures; moderate experiences may cause some interference with functioning
- SEVERE: Events interrupt the participant's normal daily activities and generally require systemic drug therapy or other treatment; they are usually incapacitating

---

### 8.3.3.2 RELATIONSHIP TO STUDY INTERVENTION

All adverse events (AEs) must have their relationship to study intervention assessed by the clinician who examines and evaluates the participant based on temporal relationship and his/her clinical judgment. The degree of certainty about causality will be graded using the categories below. In a clinical trial, the study product must always be suspect.

- DEFINITELY RELATED: The adverse event is clearly related to the investigational agent/procedure – i.e. an event that follows a reasonable temporal sequence from administration of the study intervention, follows a known or expected response pattern to the suspected intervention, that is confirmed by improvement on stopping and reappearance of the event on repeated exposure and that could not be reasonably explained by the known characteristics of the subject's clinical state.
- POSSIBLY RELATED: An adverse event that follows a reasonable temporal sequence from administration of the study intervention follows a known or expected response pattern to the suspected intervention, but that could readily have been produced by a number of other factors.
- NOT RELATED: The adverse event is clearly not related to the investigational agent/procedure - i.e. another cause of the event is most plausible; and/or a clinically plausible temporal sequence is inconsistent with the onset of the event and the study intervention and/or a causal relationship is considered biologically implausible.

---

### 8.3.3.3 EXPECTEDNESS

The principle investigator along with co-investigators will be responsible for determining whether an adverse event (AE) is expected or unexpected. An AE will be considered unexpected if the nature, severity, or frequency of the event is not consistent with the risk information previously described for the study intervention.

- UNEXPECTED - nature or severity of the event is not consistent with information about the condition under study or intervention in the protocol, consent form, product brochure, or investigator brochure.
- EXPECTED - event is known to be associated with the intervention or condition under study.

---

### 8.3.4 TIME PERIOD AND FREQUENCY FOR EVENT ASSESSMENT AND FOLLOW-UP

The occurrence of an adverse event (AE) or serious adverse event (SAE) may come to the attention of study personnel during study visits and interviews of a study participant presenting for medical care, or upon review by a study monitor.

All AEs including local and systemic reactions not meeting the criteria for SAEs will be captured on the appropriate case report form (CRF). Information to be collected includes event description, time of onset, relationship to study product (assessed only by those with the training and authority to make a diagnosis), and time of resolution/stabilization of the event. All AEs occurring while on study must be documented appropriately regardless of relationship. All AEs will be followed to adequate resolution.

Any medical condition that is present at the time that the participant is screened will be considered as baseline and not reported as an AE. However, if the study participant's condition deteriorates at any time during the study, it will be recorded as an AE.

Study research technicians will record all reportable events via daily telephone visits with start dates occurring sometime near 24 hours after informed consent is obtained and continue until 2 days (for non-serious AEs and SAEs) after the last planned day of study drug administration (total of 7 days). At each study visit, study research technicians will inquire about the occurrence of AE/SAEs since the last visit. Events will be followed for outcome information until resolution or stabilization.

Solicited events will include patient self-reported:

- Nausea
- Vomiting
- Indigestion
- Worsening of shortness of breath or difficulty breathing
- Allergic reaction
  - skin rash
  - hives
  - swelling of lips or tongue
- Hospitalized or physician visit for study drug related adverse effect

Unsolicited events will include any patient self-reported adverse event that is provided without prompting by the research technician and that is not related/similar to any of the solicited events being collected.

### 8.3.5 ADVERSE EVENT REPORTING

[figure not shown]
Formal data safety monitoring will occur every two weeks by an Independent Safety Monitor. A review of events necessitating unblinding of study subjects, overall rate of solicited and unsolicited adverse events, as well as the rate of patient reported self-dropout due to intolerance will be continuously monitored throughout the study period. If the overall dropout rate exceeds 10% at any time or a study subject experiences a serious adverse event the Investigational Review Board (IRB) will be notified within five business days for review. The study period will be terminated early if the IRB, Independent

Safety Monitor, or study investigators determine that the study jeopardizes patient safety beyond an expected risk level at any time.

#### 8.3.6 SERIOUS ADVERSE EVENT REPORTING

The study research team including technicians and co-investigators will immediately report to the primary investigator and Independent Safety Monitor any serious adverse event, whether or not considered study intervention related, including those listed in the protocol and must include an assessment of whether there is a reasonable possibility that the study intervention caused the event (a physician research team member must determine probability of adverse event occurring due to study drug). Study endpoints that are serious adverse events (e.g. hospitalization for either a suspected study drug related adverse event or worsening respiratory status from viral infection) must be reported in accordance with the protocol unless there is evidence suggesting a causal relationship between the study intervention and the event (e.g., hospitalization from anaphylaxis). In that case, members of the research team or other involved party such as the investigational drug pharmacist in cases of unblinding must report the event to the primary investigator and Independent Safety Monitor within 24 hours. The primary investigator must report any unexpected serious adverse event to the IRB within 5 business days. All serious adverse events (SAEs) will be followed until satisfactory resolution or until the site investigator deems the event to be chronic or the participant is stable.

The primary investigator will be responsible for notifying the Food and Drug Administration (FDA) of any unexpected fatal or life-threatening suspected adverse reaction as soon as possible, but in no case later than 5 business days after the primary investigator's receipt of the information. In addition, primary investigator must notify FDA and all participating investigators in an Investigational New Drug (IND) safety report of potential serious risks, from clinical trials or any other source, as soon as possible, but in no case later than 5 business days after the primary investigator determines that the information qualifies for reporting. See below flow chart for serious adverse event reporting scheme:

### 8.3.7 REPORTING EVENTS TO PARTICIPANTS

Patients will not be informed of adverse events apart from those self-reported by them during secondary endpoint data collection. Incidental findings from study enrollment will be communicated via telephone contact to study patients as part of routine care follow-up and in accordance with MUHC emergency department procedures.

### 8.3.8 EVENTS OF SPECIAL INTEREST

A separate study is planned that will collect blood samples in 10 patients to assess serum concentrations of zinc and EGCG, and a complete metabolic panel (CMP) following five days of taking study drug. Patients will be selected using the same criteria as those enrolled in the placebo-controlled trial, but will not be randomized to blinded treatment given the logistical requirements necessitating accurate blood sampling. These patients will also not be a part of primary and secondary endpoint collection via daily telephone visits. The purpose of this study is to simply describe peak serum levels of zinc and EGCG following multiple dosing of the study drug, as well as to assess the rate of transaminitis if any is to occur. Occurrences of transaminitis for which the alanine transaminase (ALT) is  $>3$ x the ULN AND the total bilirubin is  $>2$ xULN will prompt reporting to the FDA within 5 business days. A separate consent form will be used for this aspect of the research.

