## 1.2 SCHEMA

### 1.3 SCHEDULE OF ACTIVITIES (SOA)

Procedures	Screening/Enrollment/ Baseline Visit 1, Day 1	Study Visit 2, Day 2	Study Visit 3, Day 3	Study Visit 4, Day 4	Study Visit 5, Day 5	Study Visit 6, Day 6	Study Visit 7, Day 7	Study Visit 8, Day 8
Informed consent	X							
Demographics ‡	X							
Medical history ‡	X							
Randomization	X							
Administer study intervention	X-----X							
Daily telephone visits for collection of study endpoints	X-----X							
Concomitant medication review	X-----X							
Physical exam (including height and weight) ‡	X							
Vital signs ‡	X							
Height ‡	X							
Weight ‡	X							
Hematology ‡	X							
Serum chemistry ‡ a	X							
EKG (as indicated) ‡	X							
Adverse event review and evaluation	X-----X							
Radiologic/Imaging assessment ‡	X							
Other assessments (e.g., immunology assays, pharmacokinetic) ‡	X							

‡ - Indicates procedures done as part of routine care and not specific to study methods

a – Basic metabolic panel or complete metabolic panel

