A separate study is planned that will collect blood samples in 10 patients to assess serum concentrations of zinc and EGCG, and a complete metabolic panel (CMP) following five days of taking study drug. Baseline serum zinc levels will be collected at time of study enrollment in the MUHC ED while post-treatment serum concentrations of zinc and EGCG will be obtained on the fifth day of taking study drug. Patients will be instructed to report to the MUHC emergency department approximately two hours following taking a dose of study drug to have their blood drawn for the aforementioned testing. CMP assays will be processed locally at MUHC while serum zinc samples will be sent to Mayo Clinic, and EGCG samples will be sent to the University of Missouri Metabolomics Center for analysis. Patients will be selected using the same criteria as those enrolled in the placebo-controlled trial, but will not be randomized to blinded treatment given the logistical requirements necessitating accurate blood sampling. These patients will also not be a part of primary and secondary endpoint collection via daily telephone visits. The purpose of this study is to simply describe peak serum levels of zinc and EGCG following multiple dosing of the study drug, as well as to assess the rate of transaminitis if any is to occur. A separate consent form will be used for this aspect of the research.

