Safety and toxicity data on EGCG have been thoroughly summarized by formal drug safety panels including the European Food and Safety Authority (EFSA) and United States Pharmacopeia Convention (USP). Common mild side effects reported with standard dosing include gastrointestinal symptoms especially when taken in a fasting state, but rare cases of hepatotoxicity have been reported. The EFSA and USP concluded that doses equal to or greater than 800mg of EGCG per day taken for four months or longer are associated with elevations of alanine aminotransferase (ALT) and aspartate transaminase (AST) in a small percentage (less than 10%) of the population. The strongest evidence for safety and hepatotoxicity risk of EGCG comes from the Minnesota Green Tea Trial (MGTT). This was a randomized, placebo-controlled, double-blind trial investigating the effects of daily EGCG (843 mg/day) for 12 months in 1075 post-menopausal women. 538 subjects were randomized to EGCG and the difference in biomarkers for the development of breast cancer was compared against placebo (n=537). The most common side effect reported that occurred significantly more often than placebo was nausea (10.2% vs 4.8%, p =0.001), while no differences were seen in rates of serious adverse events (2.2% vs 1.5%). Liver enzyme elevations in patients taking EGCG occurred more frequently compared to placebo (6.7% vs 0.7%, p < 0.001), however, the average increase in ALT was only 5.4 U/L and was reversible after stopping therapy. Overall, green tea extracts are generally considered safe for human consumption with liver injury occurring rarely with doses less than or equal to 800 mg/day of EGCG and taken less than two weeks in duration.

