#### 5.2 EXCLUSION CRITERIA

An individual who meets any of the following criteria will be excluded from participation in this study:

1. Pregnant or actively seeking to become pregnant
2. Positive for influenza with planned treatment with oseltamivir or baloxavir
3. Current or planned treatment with an FDA regulated drug (including those under EUA) for COVID-19
4. Chronic liver disease (i.e. baseline liver function tests (LFTs) > 1.5x the ULN or established cirrhosis)
5. Chronic renal failure stage 4 or greater
6. History of kidney stones
7. Acute secondary bacterial infection at the time of enrollment
8. Requiring hospitalization for any reason at the time of enrollment
9. History of copper or iron deficiency
10. Current prescription for quinolone antibiotics, tetracycline antibiotics, or penicillamine at the time of enrollment

11. Allergy/intolerance to any of the active ingredients under investigation including zinc citrate, green tea extract, and ascorbic acid (vitamin C)
12. Patients without decision making capacity
13. Currently enrolled in another clinical trial for a respiratory viral infection

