### 7 STUDY INTERVENTION DISCONTINUATION AND PARTICIPANT DISCONTINUATION/WITHDRAWAL

#### 7.1 DISCONTINUATION OF STUDY INTERVENTION

Discontinuation from study supplement or placebo does not mean discontinuation from the study, and remaining study procedures should be completed as indicated by the study protocol. If a clinically significant finding is identified (including, but not limited to changes from baseline) after enrollment, the investigator or qualified designee will determine if any change in participant management is needed. Any new clinically relevant finding will be reported as an adverse event (AE).

Adverse events necessitating discontinuation from the study including removing patients from follow-up telephone visits for any remaining outcome related data collection include any event that would lead to a patient requiring hospitalization. This includes hospitalization related to a suspected adverse event from study drug resulting in unblinding procedures or for worsening respiratory status. Patient self-discontinuation of study intervention due to intolerance affecting future compliance will allow patients to remain in the study to complete any remaining telephone visits for primary and secondary endpoint data collection. Efforts to promote compliance including reinforcing patients to administer study product two hours following a meal will be employed before discontinuing patients from study intervention, but patient refusal to continue with treatment will be considered a dropout with an attempt to collect remaining telephone visits for completeness of endpoint related data capture.

The data to be collected at the time of study intervention discontinuation will include the following:

- Date of study discontinuation
- Reason for discontinuation
- Number of study days completed prior to discontinuation of treatment/study withdrawal
- Total number of patient-reported doses taken of study drug prior to discontinuation of treatment/study withdrawal

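### The ten-patient cohort is to yield a transaminitis rate from one day-five panel, with no required Day 1 ALT and no control group

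*Combined protocol and SAP*

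**What the plan says.** Sections 4.1 and 8.3.8 describe a separate study of ten patients, chosen by the same criteria as the trial and with its own consent form. Part of its purpose is "to assess the rate of transaminitis if any is to occur". The complete metabolic panel (CMP) comes after five days of dosing. For the start of dosing, section 4.1 names one sample: "Baseline serum zinc levels will be collected at time of study enrollment in the MUHC ED". Section 6.1.2 states that these patients are neither randomized nor given placebo.

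In section 1.3, Day 1 serum chemistry carries the footnote "Basic metabolic panel or complete metabolic panel" and a symbol whose legend reads "Indicates procedures done as part of routine care and not specific to study methods". Section 8.1 likewise leaves emergency department laboratory work to routine care.

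Exclusion 4 (section 5.2) defines chronic liver disease as "baseline liver function tests (LFTs) > 1.5x the ULN or established cirrhosis".

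Section 8.3.8 gives one numerical liver rule: ALT above 3 times ULN together with total bilirubin above 2 times ULN goes to the FDA within 5 business days. It gives no cut-off for transaminitis itself.

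**The concern.** A rate of transaminitis on study drug needs either a starting value or a comparison group. The cohort has no comparison group and the documents require no starting value. If day-five ALT is raised, the cause may be the product, earlier liver disease or the acute infection, and a single value cannot show even whether the rise came before the first dose.

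These ten panels are the only on-treatment liver tests in the documents. The section 1.3 schedule has chemistry on Day 1 only, and the safety items in section 8.2 are symptoms and medical visits. The question is one that the protocol itself raises. The daily dose is 1,600 mg of extract at 50% EGCG or more, so about 800 mg of EGCG, and section 4.3 links that level to enzyme elevations when taken for four months or longer.

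A second consequence concerns eligibility. Exclusion 4 turns on a laboratory value that no procedure obliges anyone to obtain, in the cohort or in the randomized trial.

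**Working it through.** **The plan's own figure.** The cohort size of ten has no stated calculation, so there is nothing to reproduce. The one computed sample size (section 9.2: 60% versus 30%, 80% power, two-sided 0.05) reproduces as 42 per arm, 84 in total. It does not bear on this point.

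**Where a Day 1 ALT could come from.**
- Cohort sampling (4.1, 8.3.8): zinc at enrollment; zinc, EGCG and CMP on day five. No enrollment ALT is named.
- Schedule (1.3): a basic panel satisfies footnote a. That a basic panel lacks ALT, AST and bilirubin is standard laboratory usage, taken here as an assumption because the documents do not say it.
- Eligibility (5.2, item 4): uses baseline liver tests but orders none.
- Baseline characteristics (9.4.5): no liver value is listed.

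So an ALT exists on Day 1 only if the emergency department happens to run a CMP or liver panel.

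**The missing cut-off.** Exclusion 4 admits values up to 1.5 times ULN. An eligible patient at 1.4 times ULN on both days is a case if the cut-off is ULN and not a case if it is 3 times ULN.

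**Effect of one pre-existing elevation (exact binomial 95% limits).**
- 0 of 10: upper limit 1 − 0.025^(1/10) = 30.8%.
- 1 of 10: lower limit 1 − 0.975^(1/10) = 0.3%; upper limit, the 97.5% point of Beta(2, 9), = 44.5%.
- If that patient was above ULN at enrollment, the other nine are at risk and 0 of 9 has upper limit 1 − 0.025^(1/9) = 33.6%.

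This contrast applies to a cut-off at or near ULN. With a cut-off of 3 times ULN, a patient already above it at entry would have been ineligible.

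**How likely such a patient is.** The documents give no rate of raised ALT among adults arriving with a respiratory infection. For an assumed share q, the chance of at least one in ten is 1 − (1 − q)^10:

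| q (assumed) | Chance of at least one in ten |
|---|---|
| 2% | 18% |
| 5% | 40% |
| 10% | 65% |
| 20% | 89% |

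For scale, the 12-month EGCG trial cited in section 4.3 had liver enzyme elevations in 6.7% on EGCG and 0.7% on placebo. The same formula gives 50% and 7%. Those are 12-month rates in post-menopausal women, so they do not predict this cohort.

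**What a Day 1 value adds.** It gives ten paired changes. The 95% half-width for the mean change is t(0.975, 9)/√10 × SD = 2.262/3.162 × SD = 0.715 × SD. For an assumed SD of 5, 10 or 15 U/L this is 3.6, 7.2 or 10.7 U/L. The cited trial reports that "the average increase in ALT was only 5.4 U/L and was reversible after stopping therapy". Ten pairs would therefore estimate a change of that size poorly unless the SD were small. The main gain is at patient level: whether each day-five elevation was there at the start.

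**The case against.** The cohort is a separate study. Its consent form is outside this document and its laboratory form is not reproduced, while the section 1.3 schedule is built around randomization and telephone visits that the cohort does not have. A baseline CMP may be specified elsewhere. That possibility stands, but sections 4.1 and 8.3.8 set out the sampling and name only zinc at enrollment.

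The aim is descriptive, n is ten, and a baseline cannot separate drug effect from illness that develops after Day 1. This too stands, and it limits the gain. A descriptive rate still needs a definition and a starting point.

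Four stronger readings are tempting, and the documents do not support them.
- *Exclusion 4 and footnote a contradict each other.* Footnote a says which routine chemistry is accepted and does not bar liver tests. Section 2.3.1 describes the exclusion as a history of chronic liver disease, so it can be applied from history plus any results to hand. This is a gap in wording.
- *The adverse event rules require a Day 1 ALT.* Section 8.3.4 says "Any medical condition that is present at the time that the participant is screened will be considered as baseline and not reported as an AE", and section 7.1 speaks of new clinically relevant findings. Both are generic. Applying them to ALT is a reasonable inference, and 8.3.3.2 offers a possibly-related category when cause is unclear.
- *The main liver safeguard fails for everyone on active product.* Section 2.3.1 puts short duration and dose first and adds the exclusion after them.
- *FDA reporting is impaired.* Its trigger uses multiples of ULN and needs no baseline.

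**Conclusion.** The point holds for the cohort. As written, the plan can produce a day-five elevation with no starting value, no control and no agreed definition of a case. It can also leave the liver-test part of exclusion 4 unchecked in any patient without liver tests.

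One misclassified patient moves the reported rate by 10 percentage points, but the exact intervals overlap heavily and no stated decision depends on the difference. How often this would happen is unknown, since the values of q and the SDs are assumed. The number of patients who might enter against exclusion 4 cannot be estimated either: the documents give neither the share without liver tests nor the share with unrecognized elevations.

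A reader might infer that all 100 randomized patients need a mandatory liver panel. The documents do not support that: the transaminitis aim belongs to the cohort, and for the randomized trial rewording the criterion is enough. This is a cheap improvement to a small descriptive safety study.

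**What to change.** 1. In sections 4.1 and 8.3.8, draw a CMP at enrollment with the baseline zinc sample and again on the fifth day of dosing in the ten cohort patients.
2. In section 8.3.8, list each patient's Day 1 and day-five ALT, AST and total bilirubin with the change. Count as treatment-emergent an ALT above ULN on day five that was at or below ULN at enrollment. Report ALT above 3 times ULN separately. The listing of changes will show any worsening in a patient who starts between ULN and 1.5 times ULN. Leave the FDA reporting rule as it is.
3. For the randomized trial, reword exclusion 4 to agree with footnote a: *known chronic liver disease or established cirrhosis, or LFTs >1.5x ULN where measured*.

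The cost is ten extra local CMPs on a draw already planned, recorded on the separate laboratory form in section 10.1.9.1. An occasional cohort patient may be excluded, or stopped under section 8.1 if the result arrives after dispensing, for an incidental rise; in the latter case some doses may already have been taken. No added test is required of randomized patients, and no sample size or primary analysis changes.
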